6.4 Treatment blinding

This is a subject and investigator-blinded study. Subjects and investigators will remain blinded to study treatment throughout the study, except where indicated below.

The identity of the treatments will be concealed by the use of study drugs that are all identical in packaging, labeling, schedule of administration, appearance, and odor.

Site staff

With the exception of any unblinded site staff identified below, all site staff (including study investigator and study nurse) will be blinded to study treatment throughout the study.

Unblinding a single subject at site for safety reasons (necessary for subject management) will occur via an emergency system in place at the site (see [Section 6.7](#)).

Drug product will be supplied as single blind patient specific kits, so an unblinded pharmacist who is independent of the study team will be required in order to maintain the blind. This unblinded pharmacist will receive treatment allocation cards from Drug Supply Management with the appropriate treatment allocation numbers. Appropriate measures must be taken by the unblinded pharmacist to ensure that the treatment assignments are concealed from the rest of the site staff.

Sponsor staff or delegate

The following unblinded sponsor roles are required for this study:

- unblinded field monitor(s)
- unblinded sample analysts (PK, PD)

The unblinded field monitors are required to review drug accountability and allocation at site. The unblinded monitors are not provided with a randomization list directly but will be unblinded through review of source documentation compiled by the unblinded pharmacist,

which details treatment allocation to individual subjects. The unblinded monitors will also be able to review the treatment allocation cards/randomization list provided to the unblinded pharmacist. The names of the unblinded monitor(s) are to be detailed in the Monitoring Plan.

The sample analysts will receive a copy of the randomization schedule (via request to the Randomization Office), to facilitate analysis of the samples. The sample analysts will provide the sample data to the study team under blinded conditions unless otherwise allowed.

The study statistician will be able to access the randomization list for interim analyses and is allowed to share unblinded information with the rest of the clinical team as appropriate for internal decision purposes, as outlined in [Table 6-3](#). For example, unblinded summaries and unblinded individual data can be shared with the team for interim analyses.

Study programmers and other personnel involved in study data analysis (e.g. Commercially Confidential Information) are allowed to access treatment assignment information for the purpose of conducting interim analyses.

The clinical trial team is allowed to share unblinded results with other sponsor staff (e.g. decision boards) as required for internal decision making on the study or the project at the time of interim analyses while the study is ongoing.

All unblinded personnel will otherwise keep randomization lists and data or information that could unblind other study team members confidential and secure except as described above.

Following final database lock all roles may be considered unblinded.

Table 6-3 Blinding levels

Role	Time or Event			
	Randomization list generated	Treatment allocation & dosing	Safety event (single subject unblinded)	Interim Analysis
Subjects/Patients	B	B	UI	B
Site staff	B	B	UI	B
Unblinded site staff (see text for details)	B	UI	UI	UI
Drug Supply and Randomization Office	UI	UI	UI	UI
Unblinded sponsor staff (see text for details)	B	B	UI	UI
Statistician/statistical programmer/data analysts	B	B	UI	UI
All other sponsor staff not identified above	B	B	UI	UI

B Remains blinded

UI Allowed to be unblinded on individual patient level

6.5 Treating the subject

AFQ056 or placebo will be administered to the subject via oral route of administration.

On the first day of each up-titration dosing and on days that PK samples are scheduled, the subject will be required to not take the medication before the visit, as it will be administered by the site personnel. Study medication (AFQ056/placebo) will be administered to subjects with solid food (i.e. breakfast /morning meal) in the morning and in the evening (i.e. dinner/evening meal).

On other days where no visits are scheduled at site, study treatment administration will occur at home/outpatient basis See the SOM for further details.

Sponsor qualified medical personnel will be readily available to advise on trial related medical questions or problems.

6.6 Permitted dose adjustments and interruptions of study treatment

Study treatment dose adjustments and/or interruptions are not permitted.

6.7 Emergency breaking of assigned treatment code

Emergency unblinding must only be undertaken when it is essential to treat the subject safely and efficaciously. Most often, study treatment discontinuation and knowledge of the possible treatment assignments are sufficient to treat a study subject who presents with an emergency condition. A complete set of emergency code break cards will be provided to the investigator site(s) and a complete set will be available at Novartis. All code break cards must be retained until the end of the study and returned to Novartis. They must be stored in a secure place but be accessible to the investigator 24 hours per day in case of emergency. The investigator will receive a blinded code break card for each subject, with the details of study treatment covered by a removable, scratch-off cover. In an emergency, the scratch-off cover can be removed to determine the treatment. The scratch-off covers are not to be removed for any reason other than an emergency. When the investigator removes the scratch-off cover he/she must note the date, time, and reason for removing it and retain this information with the case report form documentation. The unblinded treatment code must not be recorded on the CRF. The investigator must also immediately inform the study monitor that the code has been broken.

It is the investigator's responsibility to ensure that there is a dependable procedure in place to allow access to the code break cards at any time in case of emergency. The investigator will need to provide:

- protocol number
- study drug name (if available)
- subject number.

In addition, the investigator must provide oral and written information to inform the subject how to contact his/her backup in cases of emergency when he/she is unavailable to ensure that un-blinding can be performed at any time.

An assessment will be done by the appropriate site personnel and sponsor after an emergency unblinding to assess whether or not study treatment should be discontinued for a given subject.

6.8 Treatment exposure and compliance

The investigator must promote compliance by instructing the subject to take the study treatment exactly as prescribed and by stating that compliance is necessary for the subject's safety and the validity of the study. The subject must also be instructed to contact the investigator if he/she is unable for any reason to take the study treatment as prescribed.

Compliance will be assessed by the Investigator and/or study personnel at each visit using pill counts and information provided by the subject. This information should be captured in the source document at each visit.

The subjects will also be instructed to bring back used packaging and unused medication at each visit for drug accountability checking. Subjects will be provided with individual Medication Diary (paper version) to record each administration of study. This record will be checked regularly (at least weekly) by site staff.

All study treatment dispensed and returned must be recorded in the Drug Accountability Log.

For the titration of the study medication, the investigator should provide clear instruction along with the dispensed medication in order to comply with the dosing titration schedule. Actual study medication intake by the subject (recorded during site administration or Medication Diary) and all titrated dose (up-titration to 200 mg bid) during the study must be recorded on the Dosage Administration Record CRF.

6.9 Recommended treatment of adverse events

Patients in the study may develop symptoms that normally appear in CUD, however an increase in these symptoms is not expected. If during the study symptoms occur that are severe enough to interfere with the activities of daily living of the patients, they should be treated according to current clinical practice:

If patients develop adverse events such as hallucinations, agitation, delirium and/or confusion medical supervision should be implemented, and if severe enough to warrant pharmacological intervention then antipsychotic medication can be given, along with the discontinuation of study medication following the follow-up period, where possible.

Medication used to treat AEs must be recorded on the Concomitant medications/Significant non-drug therapies CRF.

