2.3 Exploratory objective(s)

Commercially Confidential Information

from cocaine use. For all examinations to be done at baseline, refer to the [Assessment schedule](#).

Treatment (days 1-98): following baseline, on Day 1, approximately 60 eligible patients will be randomly assigned in a 1:1 ratio to either AFQ056 or placebo

- Group A - AFQ056: up-titration regimen for the first 2 weeks (14 days): 50 mg bid from Day 1 to Day 7 , 100 mg bid from Day 8 to Day 14 , followed by dosing at 200 mg bid for 84-days
- Group B: matching placebo.

Study drug: must be taken twice daily (bid) in the morning and evening (separated by approximately 12 hour intervals) with food. For all ambulatory morning visits that involve any study assessments or PK/urine sample collection, study medication will be self-administered by patient at study center and supervised by study personnel. On these days, standard breakfast should be served at study center and consumed by the patient during his/her medication intake.

During treatment period, patients will also undergo assessments with various scales and questionnaires, as well as safety assessments and pharmacokinetic sampling at pre- and 2 ± 1 -hour post dose per SoA. For a detailed outline of all study assessments and time points refer to the [Assessment schedule](#).

Urine samples (days1-113): samples will be collected at study center twice per week, with at least 48 hours separating tests. The sample collection will be assayed quantitatively for the presence of cocaine's metabolite (benzoylecgonine (BE)), as well as, other illicit drugs may be assayed. It is expected that a total of approximately 33 urine samples will be collected during study conduct: 28 samples from patients who remain in treatment for the 14 weeks (total of 4 samples: weeks 1–2 of up-titrations); 24 samples in weeks 3–14 (maintenance dose); 4 samples in weeks 15–16 (follow up) and finally 1 last sample at end of study visit. If a patient fails to attend the clinic or refuses to provide a sample on a scheduled testing day, samples will be considered positive unless an excused absence is granted (e.g.. illness, other personal reason). In cases of missed or refused samples, samples should be collected on the next day whenever possible.

Clinical support to ensure medication and protocol's adherence:

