5.2 Prohibited treatment

Use of the following treatments/therapies are NOT allowed during the study:

- **Cognitive Behavioral Therapy (CBT)** or other similar interventional behavioral therapy(ies). Group therapies and support groups (such as AA) are allowed, provided the patients have been on such therapies for at least 3 months before screening, and therapies are continuing during the conduct of the study.
- **Glutamatergic drugs** due to potential mechanistic interactions with AFQ056
- **Moderate or strong inducers/inhibitors of CYP3A4** – potential for increased/decreased metabolism of AFQ056 (see [Section 17](#))
- **Lithium**– narrow therapeutic windows and not enough data regarding potential interactions between AFQ056 and these compounds
- **Unstable** treatment (unstable dose) with domperidone, antidepressants, and anxiolytics (see below *) – multiple potential interactions confounding the safety of AFQ056, especially when doses are adjusted
- Typical or atypical neuroleptic agents – risk of malignant neuroleptic syndrome when dopaminergic medication is adjusted
- Any pharmacotherapy with a potentially effective drug for cocaine dependence (i.e. disulfiram, acamprosate, methyl phenidate, modafinil, topiramate, immediate-release dexamfetamine, or baclofen) – potential for confounding the safety and/or efficacy of AFQ056

Notes:

SSRI are not allowed unless patients are on stable dose regimen and this dose is maintained over Screening and Baseline and being maintained stable during the treatment period.

Short-acting benzodiazepines used occasionally (e.g. against insomnia) are permitted

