6.10 Rescue medication

Rescue medication should be given according to clinical practice, and it should be documented

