7.2 Discontinuation of study treatment

Discontinuation of study treatment for a subject occurs when study treatment is stopped earlier than the protocol planned duration. Discontinuation of study treatment can be decided by either the subject or the investigator.

Discontinuation of study treatment and patient withdrawal will be at the discretion of the Investigator, under the following circumstances:

- Moderate and persistent (>24 hours) CNS related AEs, i.e.. behavioral effects and/or neurological adverse effects, in the opinion of the Investigator as suspected to be related to AFQ056 study medication
- Missed > 6 consecutive visits
- Missed > 7 consecutive doses of study medication during the fixed-dose treatment period or a total of more than 14 cumulative doses at any time during the study
- Use any of prohibited treatment

* If a liver or renal event occurs, follow guidelines outlined in [Appendix 2](#) regarding discontinuation of study treatment.

Study treatment **must be** discontinued under the following circumstances:

- Subject/guardian decision - subjects may choose to discontinue study treatment for any reason at any time.
- The investigator believes that continuation would negatively impact the safety of the subject or the risk/benefit ratio of trial participation.
- Any protocol deviation that results in a significant risk to the subject's safety.
- Pregnancy (see [Section 8.6](#) (Safety) and [Section 9.6](#) (Pregnancy reporting)).
- Severe withdrawal syndrome or need for detoxification

For all discontinued patients, the follow-up period is to be followed, where possible.

Patients, who discontinue study treatment must NOT automatically be considered withdrawn from the study. Patients who discontinue study treatment before completing the study, and those who prematurely withdraw from the study for any reason, must be scheduled for a visit approximately 1 week after the last dose of study medication, at which time all of the assessments listed for the final visits (End of Study visit) must be performed (see [Assessment schedule](#)).

After study treatment discontinuation, at a minimum, the following data should be collected at clinic visits or via telephone/email contact:

- new / concomitant treatments
- adverse events/Serious Adverse Events

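### Protocol 5.2 prohibits neuroleptics and 6.9 permits antipsychotics for severe adverse events, with no cross-reference, a stop time that cannot work as written, and an unclear link to stopping study drug

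*Protocol*

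**What the plan says.** Protocol Section 5.2 introduces its list with "Use of the following treatments/therapies are NOT allowed during the study". One entry is "Typical or atypical neuroleptic agents – risk of malignant neuroleptic syndrome when dopaminergic medication is adjusted". The section writes out its exceptions: established group therapy or support groups, SSRIs at a stable dose, and occasional short-acting benzodiazepines. It has none for treating an adverse event.

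Section 6.9 covers patients who develop confusion, delirium, agitation or hallucinations. It asks for medical supervision and, where the event is severe enough to need drug treatment, states that "antipsychotic medication can be given, along with the discontinuation of study medication following the follow-up period, where possible". It does not refer to 5.2.

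Section 7.2 introduces a list of discretionary grounds with "Discontinuation of study treatment and patient withdrawal will be at the discretion of the Investigator, under the following circumstances". That list includes use of a prohibited treatment, and moderate, persistent CNS events suspected to be related to study drug. A separate list makes stopping mandatory, among other cases, when the investigator believes that continuing would harm the patient's safety or the risk/benefit balance. The section adds: "For all discontinued patients, the follow-up period is to be followed, where possible".

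Section 6.10 says "Rescue medication should be given according to clinical practice, and it should be documented" and names no drug.

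The study design text gives the dosing period as "Treatment (days 1-98): following baseline, on Day 1". Table 8-1 places the follow-up visits after it. Protocol Sections 11.4.1 and 11.4.3 and SAP Section 6.1.1 compute the primary variable over 98 days for completers, and up to the last dose for patients who stop treatment early.

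**The concern.** A site treating a severe event of the kind named in 6.9 gets conflicting instructions. If it gives an antipsychotic under 6.9, it breaches 5.2, which restricts that class for a stated safety reason. If it keeps to 5.2, it forgoes a treatment that 6.9 allows. The sentence that should say what happens to study drug places the stop after a period that itself begins only once dosing has ended.

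Two things are at stake. The first is patient safety: sites could manage the same acute psychiatric event differently and each cite the protocol. The second is the data: the decision to stop or continue sets the last dose, and the last dose sets the days that enter the primary variable for that patient.

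**Working it through.** The plan states no figure to reproduce. The check compares the passages and uses day arithmetic.

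**1. Ban against permission.** Section 5.2 covers the whole study and names typical and atypical neuroleptics. Section 6.9 permits antipsychotics, the same class, within the study. Section 5.2 spells out exceptions for other treatments, so an adverse-event exception cannot simply be presumed, and no cross-reference supplies one. The two sections conflict.

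**2. Timing clause in 6.9.** Inputs are the treatment arms (Section 6.2) and Table 8-1.
- Dosing: 7 days at the first step + 7 at the second + 84 at fixed dose = 98 days, so the last planned dose is on Day 98.
- Follow-up visits: Days 99, 102, 106 and 112, each ±1. End of study: Day 113 ±3, that is Day 110 to Day 116.
- End of study minus last planned dose: 110 − 98 = 12 days at the earliest, 113 − 98 = 15 nominally, 116 − 98 = 18 at the latest. SAP Section 1.4 says approximately 14 days, which is consistent.

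A stop placed after follow-up therefore falls when no study drug remains to be stopped. For a patient who stops early, follow-up comes after the stop, so a stop timed after follow-up is circular.

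**3. Likely intended sense.** The 7.2 sentence quoted above uses nearly the same words in the opposite order: a patient who has discontinued goes on through follow-up where possible. Read that way, 6.9 would mean stop, then follow up. This is an inference from the parallel wording; 6.9 does not say it.

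**4. Linked or discretionary stop.** Section 6.9 joins the antipsychotic to discontinuation. Section 7.2 puts use of a prohibited treatment among the discretionary grounds. Its mandatory safety ground applies only if the investigator holds the stated belief. Section 6.6 permits no interruption, so on these sections the choice is to continue or to stop. Step 3 repairs the timing but does not settle which of the two applies.

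**5. Effect on the primary variable.** If the event occurs on Day d and treatment stops that day, the denominator is about d days. If treatment continues to the end, it is 98 days. The difference is 98 − d. For an assumed event on Day 20, that is 98 − 20 = 78 days. This shows how one patient's value depends on the reading. It is not an estimate of bias, because the documents give neither the number of such patients, nor their timing, nor their cocaine use before and after the event.

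**The case against.** The strongest reply is that this is a wording slip with little practical effect. Section 6.9 is the specific rule for severe events and pairs the antipsychotic with discontinuation; the 7.2 sentence shows what was meant; and 7.2 already allows, or on safety grounds requires, stopping during dosing. Much of this stands. On the 7.2 reading the stopping provisions can be followed together. Section 6.10 is silent rather than contradictory: it names no drug and does not override 5.2. The reply does not remove the conflict between 5.2 and 6.9, and it does not settle whether the stop is automatic or discretionary.

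A reader might infer more than the documents support:
- *That study drug may be stopped only after follow-up, so that study drug and a neuroleptic are taken together for the rest of treatment.* Section 6.9 contains no such restriction. Prolonged joint exposure would need either the literal timing or a discretionary decision to continue.
- *That the trial expects drug-induced psychosis.* Section 6.9 does not require the event to be attributed to study drug. Section 3.7 ties visual hallucinations to single intakes at 3 to 4 times the study's highest dose and to chronic smokers. The hold criteria in 7.5 show vigilance, not an expected rate.
- *That affected patients would be mainly in the AFQ056 arm, or would number a few out of 30.* The documents give no arm-specific rate or count for this trial.

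Truncation at the last dose applies to every early stop and is a separate question. The primary model and the SAP's sensitivity and supportive analyses are redacted, so their handling of such patients cannot be judged.

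**Conclusion.** The plan is wrong as written on two points and unclear on a third. The ban in 5.2 and the permission in 6.9 contradict each other. The 6.9 timing clause cannot operate as a time, since the end of follow-up lies 12 to 18 days after the last planned dose. Whether stopping study drug accompanies antipsychotic use or is discretionary is unresolved between 6.9 and 7.2.

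This is an internal inconsistency of wording that bears on patient safety, with a secondary effect on which days are counted for an affected patient. The effect on the treatment comparison cannot be sized from the documents. The conclusion rests on the public text of these sections and on neuroleptic and antipsychotic denoting the same class. It does not rest on any assumed frequency of events or imbalance between arms.

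**What to change.** Reconcile Protocol Sections 5.2, 6.9 and 7.2 so that one rule governs antipsychotic use for adverse events and its link to discontinuation of study drug. The sponsor's clinicians must choose that rule; none is proposed here. Then:
- rewrite the timing clause in 6.9, and if the sense of 7.2 is intended, say so directly;
- add cross-references between 5.2 and 6.9, and optionally from 6.10 to 5.2.

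The cost is a protocol amendment changing a few sentences, with notice to sites. The change itself needs no new procedure, visit or data collection.

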6.10 Rescue medication

Rescue medication should be given according to clinical practice, and it should be documented

